## 8.4. Demographic and Other Baseline Characteristics

Demographic information and baseline characteristics will be summarized for the Safety analysis population by dose cohort and overall.

The number and percentage of patients will be provided for sex (male, female), ethnicity (Hispanic or Latino, Not Hispanic or Latino), race (American Indian or Alaska Native, Asian, Black or African American, Native Hawaiian or Other Pacific Islander, White, Other), and each Eastern Cooperative Oncology Group (ECOG) performance status.

Descriptive statistics will be provided for age and body mass index (BMI), weight and height, where BMI is calculated as follows:

BMI = weight(kg) / (height(m) $^2$ ).

General medical history information will be coded by System Organ Class (SOC) and Preferred Term (PT) using the Medical Dictionary for Regulatory Activities (MedDRA), version 15.0. The count and percentage of patients with each medical history event will be summarized by MedDRA SOC and preferred term for all patients only (not by dose cohort). SOCs will be presented alphabetically with PTs in descending order of frequency.

Cancer history data will be summarized as number and percentage for each type of cancer. The assessment of general medical history information will be obtained during the screening period, within 21 days before the 1st dose.

Prior medication, and prior anti-cancer regimens, along with prior response information will be listed.

Prior anti-cancer regimens and prior antineoplastic therapies (radiation and surgery) along with corresponding response data will be listed for all patients.

Prior anti-cancer regimens, and prior antineoplastic therapy of both radiotherapy and surgery will be defined as having the starting date and/or the end date (if present) of the medication before the 1st dose.

## 8.5. Extent of Exposure

There are 3 phases of the study, Vaccine Induction Phase, Consolidation Phase, and Maintenance Phase. For Vaccine Induction Phase, a patient will be given one dosage every 7 days, 5 times. For Consolidation Phase, a patient will be given one dosage every 14 days, 4 times. For Maintenance Phase, a patient will be given one dosage every 28 days until discontinuation. All patients with at least one dose will be included in the summary. The following summary statistics related to drug exposure will be calculated by treatment phase and dose cohort, overall by cohort, and overall:

- Number and percentage of patients with dose reduction, dose escalation, and no dose modification will be presented.
- Duration of exposure, by patient, defined in weeks, is calculated as Duration (weeks) = (last dose date first dose date + 1) / 7.
- Cumulative dose = sum of all doses administered.

A by-patient listing of study drug dosing based on the Safety population will be provided.

## 8.6. Analysis of Efficacy

## 8.6.1. Primary Analysis

To establish the safety and tolerability of WT2725 and to determine the MTD of WT2725 are the primary analyses of this study. For details see Section 8.7.1.

## 8.6.2. Secondary Analyses

The number and percentage of patients will be presented according to categories of irRC, IWG, and /or tumor markers of CA-125 and WT1 by RT-PCR by dose cohort displaying their best response on-study.

The baseline assessment for patients with solid tumors or AML is defined as the assessment at screening, obtained within the 28 days prior to the planned first dose of the study drug. If multiple assessments are available, the most recent one should be used.

Tumor assessments will be conducted during screening, and then every 8 weeks after the first dose of study drug. All tumor assessments may be performed within  $\pm 7$  days of the scheduled assessment but must be completed before study drug is administered. All patients should complete an End of Study visit within 28 days after the last dose of study drug and prior to the start of alternate antineoplastic therapy.

A listing of patients with nonenhancing lesion assessments will be provided.

### 8.6.2.1. Immune-related Response Criteria (irRC)

Tumor response is based on total measurable of tumor burden in patients with solid tumors (non-AML patients). For the irRC, index and measurable new lesions are taken into account. A measurable lesion is defined as 5x5 mm or more on helical Computed Tomography (CT) scan.

At the pretreatment tumor assessment, the sum of the products of the 2 largest perpendicular diameters (SPD) of all index lesions (up to 5 lesions per organ, up to 10 visceral lesions, and 5 cutaneous index lesions) is calculated.

At each subsequent tumor assessment, the SPD of the index lesions and of new, measurable lesions ( $\geq 5x5$  mm, up to 5 new lesions per organ; 5 new cutaneous lesions; and 10 visceral lesions) are added together to provide the total tumor burden:

Tumor Burden =  $SPD_{index \ lesions} + SPD_{new, \ measurable \ lesions}$ 

Percentage changes in tumor burden per assessment time point describe the size and growth of both baseline and new, measurable lesions as they appear. At each tumor assessment, the response in index and new, measurable lesions is defined based on the change in tumor burden (after ruling out immune-related progressive disease [irPD]). Decreases in tumor burden must be assessed relative to pretreatment measurements (i.e. the SPD of all index lesions at screening).

Overall response will be determined by the investigator based on tumor burden according to the irRC response assessments as follows:

- irCR (immune-related complete response) = complete disappearance of all lesion (whether measurable or not, and no new lesions) confirmed by a repeat consecutive assessment 4 weeks after the date of first documentation
- irPR (immune-related partial response) = decrease in tumor burden  $\geq 50\%$  relative to baseline confirmed by a consecutive assessment 4 weeks after the date of first documentation
- irSD (immune-related stable disease) = not meeting criteria for irCR or irPR and the absence of irPD
- irPD (immune-related progressive disease) = increase in tumor burden ≥ 25% relative to nadir (prior minimum recorded tumor burden during the study) confirmed by a repeat, consecutive assessment at least 4 weeks after the date of first documentation
- Unconfirmed irPD = Any irPD record after study day 1 and no record of irPD confirmed 4 weeks after, which include the situation that the PI can discontinue a patient from the study for the reason of PD without confirmation of PD after 4 weeks if patients have rapid symptomatic progression accompanied by a decline in performance status.

The assessment made by the investigator will be used for all summaries.

Best response is defined to be the best irRC response (irCR > irPR > irSD > irPD) evaluated after dosing until treatment discontinuation. Patients without post-baseline evaluations will be considered as unevaluable. Additional categories are defined for response (irCR + irPR) and disease control (irCR + irPR + irSD).

Tables will summarize the number and percentage of the best overall tumor response for each category by dose cohort, the number, percentage, and Wilson Score 95% CI will also be presented for the response categories of irCR, response, and disease control.

The percent change in tumor burden from baseline will be presented at each posttreatment tumor assessment graphically and in patient data listings. Percent change will be calculated as 100\*[(current tumor burden - baseline tumor burden)/baseline tumor burden]. The best change, i.e., the minimum of percent change from baseline for each patient will be displayed in a waterfall plot.

A by-patient listing of irRC assessment will be provided.

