11. AMENDMENT NO. 6, PROTOCOL VERSION 7.0 (03 DEC 2014)

The following changes were made to the protocol:

- Initial dose escalation in this study was completed, with the highest planned dose of 9.0 mg being administered without dose-limiting toxicity. This dose was anticipated to be a recommended phase 2 dose (RP2D), and additional patients were enrolled and initiated treatment at this dose. With the expanded cohorts of patients treated at 9.0 mg, no important unanticipated risks, potential risks, or safety signals have been observed; the 9.0 mg dose is not considered the maximum tolerated dose (MTD). Based on the potential of WT2725 Dosing Emulsion to be of benefit to patients and the lack of tolerability issues observed for the expansion cohorts at the RP2D of 9.0 mg a second part has been added to the study which includes 2 additional dose escalation cohorts (18.0 and 27.0 mg). These cohorts are restricted to patients with glioblastoma and acute myeloid leukemia (AML) in order to accumulate more data with these malignancy types. In order to obtain adequate data for assessment of these dose levels, pending successful DLT evaluation, enrollment in each of these 2 cohorts is open to 10 patients with at least 4 patients of each of these malignancy types in each cohort. If the MTD is reached in Part 2 before the total of 20 patients are enrolled, remaining patients will be enrolled at the prior dose level. In the event that a dose level is excluded from further study due to dose limiting toxicity all patients may continue the study at the most recently completed study

without DLT, eg, if the 27.0 mg dose is excluded due to DLT all patients may continue at 18.0 mg. Additionally, Part 2 of the study will evaluate an extended Induction Phase, ie, 8 weeks instead of 4 weeks, and an extended Consolidation Phase, ie 12 weeks instead of 6 weeks.

- The following changes to the study design were implemented for Part 2:
 - In order to prevent abrupt cessation of prior therapy that may be making an effective contribution to the management of disease, patients who have been established on treatment with hydroxyurea may continue up to one cycle of hydroxyurea following entry into this study.
 - As WT2725 Dosing Emulsion has not been shown to adversely affect hematology parameters and patients with AML are expected to have baseline leukemia-related cytopenias and often receive prophylactic antibiotics:

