In Part 2 of the study, the 18.0 mg cohort will be conducted first. After safety and tolerability have been established for the 18.0 mg cohort, enrollment of subsequent patients will be conducted sequentially in the 27.0 mg cohort. Approximately 10 patients at each dose level (18.0 and 27.0 mg) with at least 4 patients with each malignancy type (glioblastoma and acute myeloid leukemia [AML]) will be enrolled at each of these dose levels. If the MTD is reached in Part 2 before the total of 20 patients are enrolled, remaining patients will be enrolled at the prior dose level. In the event that a dose level is excluded from further study due to dose limiting toxicity all patients may continue the study at the most recently completed dose without DLT, eg, if the 27.0 mg dose is excluded due to DLT all patients may continue at 18.0 mg.

Patients who have completed the consolidation phase of their assigned cohort and have not experienced a DLT,  $\geq$  Grade 2 study drug-related injection-site reaction, or required a dose reduction may have their dose escalated to that of the highest cohort for which safety and tolerability have been established. The expected time to enroll each dose escalation cohort (2 - 6 patients) is between 6 and 12 weeks.

Each part of the study will include 3 treatment phases based on intended timing of study drug dosing as indicated below (see Figures 1 and 2):

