- Tumor assessments (per irRC for solid tumors, modified IWG for AML, and/or standard tumor markers as appropriate, and quantitative RT-PCR for WT1 transcript for AML) are not required to be repeated if they have been performed within the 28 days before first dose (there are no variations allowed beyond this window). If multiple assessments are available, the most recent ones should be used as the baseline result. Data from at least one additional historical assessment prior to the baseline assessment should also be provided, if available. Progressive disease requires confirmation by a repeat, consecutive assessment at least 4 weeks after the date of first documentation, unless rapid clinical deterioration is seen. For patients with glioblastoma, progressive disease should additionally be confirmed by SPECT, perfusion MRI, MRI spectroscopy or C-14 methionine PET or pathology from available surgical/biopsy specimens to differentiate from pseudoprogression. For patients with AML, bone marrow aspirations/biopsies are to be provided at baseline and subsequently when clinically indicated, however peripheral blood should be assessed for blasts and WT1 transcript at baseline and at least every 4 weeks or more frequently as clinically indicated.
- Tumor markers drawn from peripheral blood samples should be assessed at least every 4 weeks after the first dose but may be performed more frequently to assess response and adjust study drug administration frequency (For other tumor assessments, perform every 8 weeks after first dose or more frequently as clinically indicated).
- t Patients who do not complete the extended dosing in the Induction Phase for reasons other than intercurrent medical conditions may continue in the study and start dosing in the Consolidation phase as scheduled on Day 71, at the discretion of the investigator and the sponsor.

Table 4: Schedule of Assessments for Consolidation Phase, Maintenance Phase, and End of Study – Part 2

Consolidation Phase a,b,p										End of Study b		Follow- up
	10 th dose		11 th dose	se	12 th dose	13 th dose	14 th dose	15 th dose				
	Day 71 (±2)	Day 83	Day 85 (±2)	Day 87	Day 99 (±2)	Day113 (±2)	Day 127 (±2)	Day 141 (±2)	every 28 (+7) days	48 hours before End of Study Visit	within 28 days after last dose	every 3 months
Continuation criteria	X c		X c		X c							

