## 8.3. Analysis Populations

There are 3 planned analysis populations.

- Safety population: includes all enrolled patients who receive at least 1 dose of study drug and will be used for the analysis of all safety and efficacy data except as noted below
- DLT population: includes all patients in the Safety population who experience a DLT within the DLT evaluation period or completed the DLT evaluation without experiencing a DLT and will be used for analysis of DLT.
- Efficacy population: include all patients in the Safety population who are evaluable for response (for each irRC, IWG, CA-125 and WT1 by RT-PCR)
  - o Population for irRC response: including all the patients in the Safety population who are not AML patients and whose lesions are measureable and have at least one posttreatment assessment. (Note that any posttreatment irRC assessment is based on the baseline assessment)
  - O Population for modified IWG response: includes all the AML patients in the Safety population who have >5% marrow blasts or >50 copy/μ g RNA of quantitative RT-PCR for WT1 transcript before the first date/time of study drug and who have at least one posttreatment assessment.
  - o Population for CA-125 tumor marker: including all ovarian cancer patients in the Safety population who have a baseline CA-125 assessment and at least one assessment posttreatment.
  - Population for WT1 by RT-PCR tumor marker: includes AML patients in the Safety population who have a baseline assessment and at least one assessment posttreatment.
- Population for CTL: including all patients in the Safety population who has a baseline assessment of percentages of WT1-positive cells among CD8-positive cells and at least one post-baseline assessment

Additional populations for analyses of other tumor markers identified may be defined in a similar manner.

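### The irRC definition of a measurable lesion names only helical CT; read literally, it removes glioblastoma patients measured by MRI and leaves anywhere from 0 to 6 patients per Part 2 cohort in the response denominator

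*SAP*

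**What the plan says.** SAP section 8.6.2.1 gives the plan's only definition of a measurable solid-tumor lesion: "A measurable lesion is defined as 5x5 mm or more on helical Computed Tomography (CT) scan". Section 8.3 makes measurability a condition of entry to the irRC population, which takes Safety-population patients "who are not AML patients and whose lesions are measureable and have at least one posttreatment assessment".

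Section 8.6.2.1 also counts up to 5 cutaneous index lesions and up to 5 new cutaneous lesions in tumor burden. It repeats the 5x5 mm threshold for new lesions without naming a modality. Counts and percentages of best response go by dose cohort, with Wilson 95% intervals for irCR, response and disease control. Section 8 defines the cohort by starting dose.

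Protocol Amendment No. 6 and SAP section 4.1 restrict the 18.0 and 27.0 mg cohorts to glioblastoma and AML. The Part 2 schedule in SAP section 6.1 assigns irRC to solid tumors.

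MRI appears in the schedule footnotes only as one way to confirm progression: "For patients with glioblastoma, progressive disease should additionally be confirmed by SPECT, perfusion MRI, MRI spectroscopy or C-14 methionine PET", or pathology. Section 8.6.2 adds: "A listing of patients with nonenhancing lesion assessments will be provided". That sentence names no modality.

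**The concern.** The definition decides who is in the denominator of a secondary endpoint, and it recognises one type of scan. A patient whose lesions are measured some other way does not meet it, whatever their size. For most tumor types this may not matter. For glioblastoma it could, because the SAP itself refers to MRI methods for that disease.

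The exposure is greatest in Part 2. Glioblastoma is the only source of irRC patients there, and because tables go by starting dose, Part 1 patients later escalated to 18.0 or 27.0 mg do not enter those columns.

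The wording is also inconsistent within its own section: cutaneous lesions count toward tumor burden, yet the definition of measurable has no place for a lesion measured on the skin.

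If the sentence stands, someone must decide how literally to take it. Section 8.2 leaves the evaluable set to be finalised as late as the data review meeting before database lock, and the study is open-label. The denominator could then be settled after responses are known.

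**Working it through.** **Inputs**

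- Part 2 cohort size: about 10 at each of two doses (SAP 4.1).
- Minimum per malignancy in each cohort: 4 glioblastoma and 4 AML (SAP 4.1).
- Share of glioblastoma patients measured by MRI alone: not given, so varied from 0% to 100%.

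**The plan's own total.** 2 cohorts x 10 = 20, which matches the total in section 4.1 ("If the MTD is reached in Part 2 before the total of 20 patients are enrolled").

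**Glioblastoma patients per Part 2 cohort.** With 10 enrolled and at least 4 of each type, the minimum is 4 and the maximum is 10 - 4 = 6. Over two cohorts that is 8 to 12.

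**Literal irRC denominator.** Let g be the number of glioblastoma patients in a cohort and s the share measured by MRI alone. The expected irRC n is g x (1 - s). If patients are independent, the chance that a cohort is empty is s^g.

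| MRI-only share s | Expected irRC n (g = 4 to 6) | Chance of an empty cohort (g = 6 to g = 4) |
|---|---|---|
| 0% | 4 to 6 | 0% |
| 50% | 2 to 3 | 1.6% to 6.3% |
| 75% | 1 to 1.5 | 18% to 32% |
| 90% | 0.4 to 0.6 | 53% to 66% |
| 100% | 0 | 100% |

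For example, at s = 50%: 4 x 0.5 = 2 and 6 x 0.5 = 3; 0.5^6 = 1.6% and 0.5^4 = 6.3%.

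These are upper values, since each patient also needs at least one posttreatment assessment.

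**What the denominator carries.** With no responders, the upper Wilson 95% limit (standard form) is z²/(n + z²), with z² = 3.84:

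- n = 4: 3.84/7.84 = 49.0%
- n = 5: 3.84/8.84 = 43.4%
- n = 6: 3.84/9.84 = 39.0%

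With n = 0 neither a percentage nor an interval exists. One responder is 1/6 = 17% of six patients but 1/3 = 33% of three, so the reading of one sentence could double a reported rate.

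**Cutaneous lesions.** No arithmetic is needed. One sentence ties measurable to CT, and the following paragraphs add cutaneous index and new lesions to the tumor-burden sum. Both cannot be followed to the letter.

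**The case against.** The strongest objection is that the modality for glioblastoma is unknown. MRI is named only for confirming progression, beside SPECT, PET and pathology, and the nonenhancing-lesion listing proves nothing about the scanner. The SAP is to be read with protocol version 7, and the protocol document available is an amendment history without the body text, so the modality may be specified there. This stands, and it is why the size is given as a range.

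Second, the sentence does not say that CT is the only acceptable method. The cutaneous lesions and the bare 5x5 mm threshold for new lesions suggest that it was not meant to exclude. The plan clearly intends irRC for glioblastoma: the Part 2 schedule says so, and Part 1 enrolls until each tumor type has at least 6 patients evaluable for DLT, biomarkers and response. This is good evidence of intent, but it does not repair the rule. A definition that names one modality gives no basis for admitting another.

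Third, the investigator's assessment is used for all summaries. That settles the response category. Section 8.3 sets population membership separately and does not defer to the investigator.

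Fourth, by-patient irRC listings and Kaplan-Meier figures repeated on the Safety population would preserve some information. This is true, but neither replaces the response and disease-control proportions.

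A reader might infer that the 18.0 and 27.0 mg irRC tables will be empty and that no solid-tumor response above 9.0 mg could be reported. The documents do not support that. It is certain only if every Part 2 glioblastoma patient is measured by MRI alone. A reader might also divide the planned glioblastoma minimums by the planned solid-tumor minimums to state a share lost across the study. Two lower bounds do not bound a ratio, and up to three RP2D cohorts of 10, each of one tumor type, could move it either way.

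**Conclusion.** The concern holds as a defect of wording that can produce a wrong denominator. Taken literally, sections 8.6.2.1 and 8.3 exclude any glioblastoma patient measured by MRI and contradict the plan's own counting of cutaneous lesions. In each Part 2 cohort the irRC denominator lies between 0 and 4 to 6, with an expected 2 to 3 if half the patients are measured by MRI alone.

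This rests on three assumptions: 10 patients per cohort, no early MTD that shifts enrollment to the lower dose, and literal application of the CT sentence. The MRI-only share is unknown. Glioblastoma patients in Part 1 face the same rule, but their number in each dose cohort is not fixed by the plan, so no figure is given for them.

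The effect is confined to the irRC analyses. The primary analyses of DLT and MTD do not use this population. The correction should be made, but it does not threaten the study's main purpose.

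**What to change.** Reword section 8.6.2.1 so that a measurable lesion is one of at least 5x5 mm on CT or MRI, or by direct measurement if cutaneous. Align it with the modality that protocol version 7 gives for each tumor type. If version 7 already names the glioblastoma modality, the SAP should follow it. In section 8.3, have the irRC population refer to this definition.

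Handle consistency of modality between baseline and follow-up in a separate assessment note. Placed inside the definition of measurability, a same-modality rule could itself exclude patients who changed scanner.

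Settle the wording before the evaluable set is finalised. The cost is a few sentences of SAP text and a check against protocol version 7. No new scans or data are needed.

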Tumor assessments will be by irRC for solid tumors, modified IWG for AML, and/or standard tumor markers as appropriate, and quantitative RT-PCR for WT1 transcript for AML. Perform every 8 weeks after first dose or more frequently as clinically indicated. Tumor markers drawn from peripheral blood samples should be assessed every 4 weeks after the first dose. This assessment may be performed ± 7 days of the scheduled assessment but must be completed before the next planned administration of study drug. For patients with AML if no other measurable disease then bone marrow aspirations/biopsies should follow the general post-transplant biopsy schedule or other clinical site guidelines. Progressive disease requires confirmation by a repeat, consecutive assessment at least 4 weeks after the date of first documentation, unless rapid clinical deterioration is seen. For patients with glioblastoma, progressive disease should additionally be confirmed by SPECT, perfusion MRI, MRI spectroscopy or C-14 methionine PET or pathology from available surgical/biopsy specimens to differentiate from pseudoprogression. For patients with AML, bone marrow aspirations/biopsies are scheduled when clinically indicated, however peripheral blood should be assessed for blasts and WT1 transcript at least every 4 weeks or more frequently as clinically indicated.

<sup>n Tumor markers drawn from peripheral blood samples should be assessed at least every 4 weeks after the first dose but may be performed more frequently (For other tumor assessments, perform every 8 weeks after first dose or more frequently as clinically indicated).

<sup>o Following the End of Study visit, patients will be contacted every 3 months to evaluate disease progression, if not already reached, and survival.

<sup>p The Consolidation Phase includes a maximum of 6 doses. Patients who do not complete the extended dosing in the Consolidation Phase for reasons other than intercurrent medical conditions may continue in the study and start dosing in the Maintenance phase as scheduled on Day 169, at the discretion of the investigator and the sponsor.

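### irSD carries no minimum time from first dose and outranks irPD, so one early on-treatment scan below the progression threshold fixes a patient as disease control, even if week 8 shows irPD that is later confirmed

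*SAP*

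**What the plan says.** SAP 8.6.2.1 assigns a category at each tumor assessment from the change in tumor burden. Complete and partial response and progression all need a repeat assessment; for irPR the wording is "confirmed by a consecutive assessment 4 weeks after the date of first documentation". irPD is a rise of at least 25% over the lowest burden recorded so far, repeated at least 4 weeks later. Stable disease is what remains: "irSD (immune-related stable disease) = not meeting criteria for irCR or irPR and the absence of irPD". It needs neither confirmation nor a minimum time.

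The patient-level summary follows from this: "Best response is defined to be the best irRC response (irCR > irPR > irSD > irPD) evaluated after dosing until treatment discontinuation". Disease control is the sum of irCR, irPR and irSD. It is tabulated by dose cohort, and the "Wilson Score 95% CI will also be presented for the response categories of irCR, response, and disease control".

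The irRC population in SAP 8.3 takes any non-AML patient with measurable lesions and one scan after treatment starts, whenever that scan falls. SAP 8.6.2 schedules scans every 8 weeks, give or take 7 days. The footnotes to the schedules in SAP 6.1 also allow earlier ones: "Perform every 8 weeks after first dose or more frequently as clinically indicated". The schedules mark a tumor assessment at the End of Study visit, and "All patients should complete an End of Study visit within 28 days after the last dose of study drug".

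**The concern.** Stable disease is the state a patient is in when treatment starts, so it says something about the drug only after enough time for an untreated tumor to grow. The SAP gives irSD no such time. A scan at week 3 or 4, perhaps ordered because someone suspected growth, can show a 20% increase and still be irSD. Because irSD ranks above irPD, that record stands as the best response whatever follows.

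The reported rate then mixes patients stable at week 3 with patients stable at week 8, and its level depends partly on when scans were done. It is shown by dose cohort with a confidence interval, so a reader will compare cohorts on it. The AML definition in SAP 8.6.2.2 does not have this weakness: disease control there is CR, CRi, PR and PRi, and unchanged disease does not count.

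**Working it through.** The documents give no disease-control rate, power or expected time to progression, so there is no plan figure to reproduce. The check is a trace of the rules, followed by an illustration.

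**Trace (8.6.2.1).** Take a burden of 100 at baseline, 120 on a clinically indicated week-4 scan, 130 at week 8, and irPD confirmed at least 4 weeks later.
- Week 4: +20% over nadir, below 25%, no response. Category irSD.
- Week 8: 130/100 = +30% over nadir. Category irPD, later confirmed.
- Best response: irSD ranks above irPD, so the patient is scored irSD and counted as disease control.

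With the week-8 scan alone, the same patient is irPD.

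**How little an early scan rules out.** With exponential growth from the baseline scan, +25% is reached by time t only if the sum of products doubles within t × ln 2 / ln 1.25. That is 9.3 weeks for t = 3, 12.4 for t = 4, 21.7 for t = 7 and 24.9 for t = 8. A tumor doubling every 15 weeks passes as stable at week 4 and fails at week 7. (Time runs from the baseline scan, which may be up to 28 days before dose 1.)

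**Size.** Assumptions, none from the documents: time to progression is exponential with median m = 8 weeks (range 6 to 12), there is no drug effect, early scans are unrelated to disease state, and an early rise of 25% or more is scored as progression. The chance of still being irSD at week t is 2^(−t/m).

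| m (weeks) | week 3 | week 7 | difference |
|---|---|---|---|
| 6 | 0.707 | 0.445 | 0.262 |
| 8 | 0.771 | 0.545 | 0.226 |
| 12 | 0.841 | 0.667 | 0.173 |

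Week 7 is the earliest in-window scheduled scan. In a group of 10 with 2 patients credited on a week-3 scan, expected disease control rises by 2 × difference / 10. That is 4.5 points at m = 8, 5.2 at m = 6 and 3.5 at m = 12. At m = 8 the rate as written is (8 × 0.545 + 2 × 0.771)/10 = 59.0%, against 54.5% if all 10 are judged at week 7.

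The worst case is that both patients would otherwise have been irPD: 2/10 = 20 points, for example from 5/10 (Wilson 95% CI 23.7% to 76.3%) to 7/10 (39.7% to 89.2%).

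**Smaller groups.** A Part 2 cohort has about 10 patients, at least 4 with glioblastoma and at least 4 with AML (SAP 4.1), so about 4 to 6 can enter the irRC analysis. One patient then weighs 1/6 to 1/4, or about 17 to 25 points.

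**Effect of the fix at m = 8.**
- If the 2 early-scanned patients also have a week-7 scan, they are judged on it and the expected rate is 54.5%.
- If the early scan is their only one, neither can count as disease control: 8 × 0.545/10 = 43.6%.
- If those shown as unevaluable (2 × 0.771 = 1.54 expected) are left out, the ratio of expected counts is 4.36/(10 − 1.54) = 51.6%.

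**The case against.** Much can be said on the other side. A patient scanned only on schedule has a first scan at about week 7 to 9, which is already a working minimum. The entry scan is never scored alone, because SAP 8.6.2.1 treats patients without a post-baseline evaluation as unevaluable. Disease control is descriptive, with no test or decision attached. The SAP also plots percent change at each assessment, lists irRC by patient, and gives Kaplan-Meier curves for PFS and TTP, so a careful reader can see the timing. An expected shift of 4.5 points is small beside a confidence interval about 50 points wide. All of this stands and limits the weight of the point. None of it removes the rule that an early irSD beats a later confirmed irPD.

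A reader might infer that cohorts with more early stops look better. The documents do not support that. Best response runs only up to treatment discontinuation, and the SAP does not say whether an End of Study scan falls inside that limit. Patients who leave without a scan are outside the irRC population and raise nothing. Scans ordered on clinical suspicion may also find more progression than the model assumes.

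A reader might also take 20 points as the likely distortion. It is the worst case for 2 patients in 10.

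Finally, the absence of irPD in the irSD definition could be read as absence at any time. The categories are assigned assessment by assessment, however, and on that reading ranking irSD above irPD would serve no purpose.

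**Conclusion.** The point holds as a gap in the definition. No section of the SAP, and nothing in the protocol's amendment history, sets a minimum time for irSD. Taken with the ranking, an early on-treatment scan can therefore outweigh a confirmed progression at the first scheduled scan.

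The text establishes the rule; the size rests on assumption. Neither the number of early scans nor the time to progression is given. Under the stated model the expected inflation is about 4.5 points (3.5 to 5.2) for 2 such patients in 10. The rate is more sensitive in the 4 to 6 non-AML patients of a Part 2 cohort. On-schedule patients, the irCR and response rates, and the DLT and MTD analyses are unaffected. The change is worth making before the data are summarized, because the cohort rates cannot otherwise be read on a common footing.

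**What to change.** Add to SAP 8.6.2.1:
- irSD counts toward best response and disease control only if documented on a scan at least 49 days after first dose. This comes from the SAP's own schedule: week 8 is 56 days after first dose, less the allowed 7.
- A patient with earlier irSD followed by confirmed irPD is scored irPD.
- A patient whose only scans are earlier and show neither response nor irPD is shown as unevaluable.
- State whether End of Study scans count toward best response.

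Keep the unevaluable patients in the main denominator, so that an early scan cannot raise the rate, and say that this is a conservative choice. It has a real cost: where the 2 patients in 10 have only the early scan, expected disease control at median 8 weeks falls from about 59% to about 44%, below the 54.5% that would be seen if all were judged at week 7. For that reason, show the rate without the unevaluable patients alongside.

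The change is a few sentences of SAP text and one extra line in the table. It needs no new data and no change to visits or treatment.
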